### 14.2.1 Pharmacodynamic Biomarkers Concentration

Population: PK/PD population

Group: Emapalumab

Contents: • Calculate the descriptive statistics of pharmacodynamic biomarkers concentration in those parameters described in Table 6 in Section 14.2 Pharmacodynamic biomarkers at each analysis time point (defined in Table 1 in Section 8.4.3 Visit Windows) by groups.

### 14.2.2 Figure of Mean $\pm$ SD of Pharmacodynamic Biomarkers Concentration Versus Time Curves

Population: PK/PD population

Group: Emapalumab

Contents:

- Create XY plots of Mean  $\pm$  SD of pharmacodynamic biomarkers concentration in those parameters described in Table 6 in Section 14.2 Pharmacodynamic biomarkers at each analysis time point (defined in Table 1 in Section 8.4.3 Visit Windows) by groups.
- X axis: Analysis visits defined in Table 1 in Section 8.4.2 Visit Windows
- Y axis: Biomarkers parameter name [unit]

#### **14.2.3      Figure of Pharmacodynamic Biomarkers Concentration Versus Time Curves of Individual Subjects**

Population: PK/PD population

Group: Emapalumab

Contents:

- Create XY plots of pharmacodynamic biomarkers concentration in those parameters described in Table 6 in 14.2 Pharmacodynamic biomarkers at actual time points by groups.
- X axis: Actual time points observed
- Y axis: Biomarkers parameter name [unit]

### **15           Safety analyses**

#### **15.1       Drug exposure**

Summaries of total dose of IMP will be presented in a listing.

## 15.2 Adverse events

Term	Definition
AE	Any unfavorable and unintended sign, (including an abnormal laboratory findings) symptom or disease, whether or not considered related to the IMP.
ADR	An adverse event whose causal relationship to the IMP cannot be ruled out.
Serious AE	Any AE occurring at any dose that in the opinion of either the investigator or sponsor results in any of the following outcomes: 1) Death, 2) Life-threatening adverse drug experience, 3) Inpatient hospitalization or prolongation of existing hospitalization (for > 24 hours), 4) Persistent or significant incapacity or substantial disruption of the ability to conduct normal life functions, 5) Congenital anomaly/birth defect, 6) Important Medical Event (IME) that may not result in death, be life threatening, or require hospitalization may be considered a serious adverse drug experience when, based upon medical judgment, it may jeopardize the subject and may require medical or surgical intervention to prevent one of the outcomes listed in this definition.
Serious ADR	A serious adverse event whose causal relationship to the IMP cannot be ruled out.
TEAE	All reported AEs that occurred after the administration of IMP up till the end of study, and those that worsened after administration of IMP.
IRR	All reported TEAEs which occurred within 24 hours from the infusion starting date/time unless the available information clearly indicates that the AE is not treatment-emergent.

All AEs occurring after IMP initiation and up to end-of study (EOS) must be recorded on specific AE forms of the eCRF. All SAEs occurring after study start (i.e., signing of informed consent) up to EOS must be reported on the SAE form and recorded in the AE pages of the eCRF.

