6.7.7.1.3 Relationship to investigational medicinal product

Each AE must be assessed by the investigator as to whether or not there is a reasonable possibility of causal relationship to the IMP administration and reported as either related or unrelated. The determination of the likelihood that the IMP caused the AE will be provided by an investigator who is a qualified physician

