8.3.8 Handling of missing data

No imputations of missing data will be performed.

9 Data collection, handling and record keeping

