## **8.6 Handling of Missing Data and Outliers**

### **8.6.1 Handling the Date of Adverse Events**

#### **8.6.1.1 TEAE**

In the case of partially or completely missing AE start date/time, the AE will be considered treatment emergent, unless the available date/time information clearly indicates that the AE started prior to start of the IMP infusion as follows:

- If the start time is missing, but start date is before start date of IMP infusion.
- If the day of the AE is missing, but the year/month are before the year/month of the start of IMP infusion.
- If the day and month of the AE are missing, but the year is before the year of the start of IMP infusion.
- If the stop date of the AE is before the start date of the IMP infusion.

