#### **8.6.1.2 IRR**

If the onset time of the AE or the start time of the infusion is missing, then an AE with an onset date equal to the infusion date or infusion date + 1 will be considered for the assessment of Infusion Related Reactions (IRRs), unless the available information clearly indicates that the AE was not treatment-emergent.

If the onset date/time of the AE is completely missing, the AE will be considered as IRR.

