#### **15.2.4 Adverse Events/Adverse Drug Reactions by Causal Relationship**

Population: Safety Analysis population

Group: Emapalumab, Placebo

Contents: 

- Calculate the number of subjects and percentages of TEAEs according to SOC/PT by groups and causal relationship to the IMP (“Not related” and “Related”).
- Each subject with multiple causal relationship to IMP in the same SOC/PT will be counted once by using the “Related” in each category.
- Denominator to calculate the percentages: The number of subjects from the population in each group.
- Conduct the same analysis for serious TEAEs.

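### The SAP's infusion related reaction table counts all early TEAEs whatever their cause, so it is sensitive but does not isolate infusion reactions, and it omits their severity

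*SAP*

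**What the plan says.** SAP 15.2 defines an IRR as "All reported TEAEs which occurred within 24 hours from the infusion starting date/time". Its only exclusion is "unless the available information clearly indicates that the AE is not treatment-emergent", which is a test of timing and not of cause.

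SAP 8.6.1.2 deals with incomplete times. If the AE onset time or the infusion start time is missing, "an AE with an onset date equal to the infusion date or infusion date + 1 will be considered", with an exception for events that are clearly not treatment-emergent. The next rule has no exception: "If the onset date/time of the AE is completely missing, the AE will be considered as IRR". SAP 8.6.1.1 does set a limit for TEAE status: an AE with missing onset is not treatment-emergent in the case "If the stop date of the AE is before the start date of the IMP infusion".

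Causality is collected. Protocol 6.7.7.1.3 has a physician investigator assess each AE, "reported as either related or unrelated". SAP 8.6.1.3 treats a missing rating on a treatment-emergent event as related, so every TEAE has a usable value for the tables.

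SAP 15.2.5 tabulates IRRs by SOC/PT, group and need for medication, and repeats this for serious IRRs. Protocol 8.3.5.2 asks for incidence and severity, including the need for medication. The protocol does not define an IRR.

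**The concern.** The label implies a causal link that the definition does not require. Unrelated early events are foreseeable in this design: valaciclovir starts on Study Day -1, subjects fast before visits, and Day 1 brings repeated blood draws through a separate line. A bruise at a sampling site that the investigator rates unrelated would still be an IRR if it began within 24 hours.

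The missing-onset rule could also bring in an event first mentioned at a late outpatient visit. Subjects stay in the unit until Day 8, so an early event should have a recorded onset. A wholly missing onset therefore seems more likely for an event recalled later, although that is an inference and not something the documents state.

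Infusion reactions are the first risk listed in protocol 4.4, so readers will look for this rate and may set it beside the earlier figure given there. What is at stake is the correct description of one safety table.

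**Working it through.** **Which planned tables could separate the events**

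- SAP 15.2.2 and 15.2.3 tabulate ADRs by SOC/PT and by intensity, with no 24-hour limit.
- SAP 15.2.4: "Calculate the number of subjects and percentages of TEAEs according to SOC/PT by groups and causal relationship to the IMP". This covers all TEAEs, again with no 24-hour limit.
- SAP 15.2.5 applies the 24-hour limit but has no causality split and no mild/moderate/severe split. Its repeat for serious IRRs does not supply severity, because protocol 6.7.7.1.2 keeps intensity and seriousness apart.
- SAP 16 plans a listing of TEAEs without specifying its columns, and no IRR listing.

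So no planned table gives related events within 24 hours, and none gives the severity of IRRs.

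**Width of the window when a time is missing**

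The fallback admits the infusion date and the next day. That runs for 48 hours minus the clock time of infusion start. Dosing is in the morning (protocol 6.7.1.3); for an assumed 09:00 start the window is 48 − 9 = 39 hours.

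**Size of one count**

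Arm sizes are 6 and 2 (SAP 4.3). One subject counted only because of an unrelated event adds 1/6 = 16.7 percentage points on emapalumab, or 1/2 = 50 points on placebo.

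**The documents' own figure**

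Protocol 4.4 gives 13 of 62 subjects with at least one IRR: 13/62 = 20.97%, which reproduces the stated 21.0%.

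**Illustration**

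Let q be the share of subjects with an unrelated TEAE within 24 hours. The documents do not give q, so it is assumed over 5% to 30%. Let p = 13/62 be the share with a true IRR, assumed to carry over and to be independent of q.

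- Chance of at least one such subject among n: 1 − (1 − q)^n. For n = 6 and q = 10%: 1 − 0.9^6 = 46.9%.
- Expected rate in the SAP table: t = 1 − (1 − p)(1 − q). For q = 10%: 1 − 0.790 × 0.9 = 28.9%.
- Part of t due only to unrelated events: (t − p)/t.

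| q (assumed) | At least 1 of 6 emapalumab | At least 1 of 2 placebo | Table rate t, emapalumab | Part of t due only to unrelated events |
|---|---|---|---|---|
| 5% | 26.5% | 9.8% | 24.9% | 15.9% |
| 10% | 46.9% | 19.0% | 28.9% | 27.4% |
| 20% | 73.8% | 36.0% | 36.8% | 43.0% |
| 30% | 88.2% | 51.0% | 44.7% | 53.1% |

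If only related events counted, the expected emapalumab rate would stay at 21.0% under the same assumptions.

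**The case against.** A prespecified all-cause window, applied alike to both arms, is a defensible and cautious convention. It catches every reaction that starts in the window. Requiring relatedness could drop a true reaction that a blinded investigator rated unrelated. The protocol gives no definition for the SAP to breach. IRR is not a named endpoint, nothing is tested, and the stopping rules use their own criteria. With 8 subjects and individual listings, a reader may be able to trace each event.

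Most of this stands. It rules out replacing the all-cause count, and it keeps the point small. It does not justify the label, the missing exception in 8.6.1.2 or the absent severity summary.

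Four stronger readings are tempting, and the documents do not support them:

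- A reader might infer that the table fails to measure infusion reactions. It includes those starting within 24 hours; its weakness is specificity.
- A reader might infer that 15.2.4 and 15.2.5 contradict each other. They answer different questions; only the IRR label makes them look inconsistent.
- A reader might infer that 8.6.1.2 breaks protocol 8.3.8, "No imputations of missing data will be performed". The IRR rule assigns a table category and fills in no date, so any conflict is weak.
- A reader might take 21.0% as a benchmark. Protocol 4.4 does not say how an IRR was defined in those trials, and dosing was repeated: 1290 infusions over 62 subjects is about 21 each, against one here.

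Relatedness also has a limit as a filter. Protocol Table 3 lists valaciclovir under an investigational product column, so a rating of related to IMP may not clearly exclude a valaciclovir reaction.

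**Conclusion.** The point holds as a matter of labelling, completeness and one loose rule. Followed exactly, the SAP would report events rated unrelated as infusion related reactions, no planned table would show the related subset within 24 hours, and the severity summary asked for in protocol 8.3.5.2 would be missing. The missing-onset sentence in 8.6.1.2 should be aligned with 8.6.1.1 and 15.2: an AE that stopped before the infusion is not a TEAE and so falls outside the 15.2 definition, but the sentence does not say so.

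The firm size is 16.7 points per subject on emapalumab and 50 on placebo. These are simply 1/6 and 1/2 and would apply to any AE row. The probabilities and expected rates rest on an assumed background rate, on carrying over the earlier 21.0% and on independence, so they show scale only. This is a cheap correction to one safety table and does not touch the primary PK/PD endpoints.

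**What to change.** 1. **SAP 15.2 and 15.2.5.** Title the all-cause table TEAEs within 24 hours of infusion start. Add a row for the subset rated related to IMP, report that row as the IRR rate, and keep the all-cause count beside it. State which product the rating refers to.
2. **SAP 8.6.1.2.** Count an AE with wholly missing onset only if the available information, such as its stop date or the visit at which it was first recorded, does not clearly place it before the infusion or outside the 24-hour window. Show such events separately.
3. **SAP 15.2.5.** Add the mild/moderate/severe split that protocol 8.3.5.2 calls for.

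The cost is SAP wording and one or two extra rows plus the severity split, all from data already collected. SAP 5.2 allows revision before database lock. The downside is some reliance on the blinded causality rating, offset by keeping the all-cause count in view.

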### **15.2.1 Adverse Events/Adverse Drug Reactions**

Population: Safety Analysis population

Group: Emapalumab, Placebo

Contents:

- Calculate the number of subjects with TEAEs and percentages by groups for the following items:
  - All TEAEs
  - ADRs
  - Serious TEAEs
  - Serious ADRs
  - TEAEs leading to drug withdrawn
  - ADRs leading to drug withdrawn
  - TEAEs leading to dose reduced
  - ADRs leading to dose reduced
  - TEAEs leading to drug interrupted
  - ADRs leading to drug interrupted
  - TEAEs leading to death
  - ADRs leading to death
- Denominator to calculate the percentage: The number of subjects from the population in each group.
- Each subject will contribute at most one count per summarization category.

### **15.2.2 Adverse Events/Adverse Drug Reactions by SOC and PT**

Population: Safety Analysis population

Group: Emapalumab, Placebo

Contents:

- Calculate the number of subjects and the percentages of TEAEs according to SOC/PT by groups.
- Contents will be sorted by SOC and PT.
- Denominator to calculate the percentages: The number of subjects from the population in each group.
- Each subject with more than one TEAE in the same SOC/PT will be counted once.
- Conduct the same analysis for ADRs, serious TEAEs and non-serious TEAEs.

### **15.2.3 Adverse Events/Adverse Drug Reactions by Intensity**

Population: Safety Analysis population

Group: Emapalumab, Placebo

Contents: 

- Calculate the number of subjects and percentages of TEAEs according to SOC/PT by groups and intensity (Mild/Moderate/Severe).
- Denominator to calculate the percentages: The number of subjects from the population in each group.
- Each subject with more than one TEAE in the same SOC/PT will be counted once by using the maximum intensity.
- Conduct the same analysis for ADRs and serious TEAEs.

#### **15.2.4 Adverse Events/Adverse Drug Reactions by Causal Relationship**

Population: Safety Analysis population

Group: Emapalumab, Placebo

Contents: 

- Calculate the number of subjects and percentages of TEAEs according to SOC/PT by groups and causal relationship to the IMP (“Not related” and “Related”).
- Each subject with multiple causal relationship to IMP in the same SOC/PT will be counted once by using the “Related” in each category.
- Denominator to calculate the percentages: The number of subjects from the population in each group.
- Conduct the same analysis for serious TEAEs.

#### **15.2.5 Infusion Related Reactions**

Population: Safety Analysis population

Group: Emapalumab, Placebo

Contents: 

- Calculate the number of subjects and percentages of infusion related reactions according to SOC/PT by groups and the need for medication (Yes/No).
- Denominator to calculate the percentages: The number of subjects from the population in each group.
- Conduct the same analysis for serious IRRs.

## 15.2.6 Deaths

Deaths will be presented in listings.

## 15.3 Laboratory data

The list of laboratory parameters evaluated in this study is presented in Table 7. Laboratory values will be classified as within range/normal, abnormal high, or abnormal low, based on the local laboratory's normal ranges for the respective parameter.

**Table 7 List of Laboratory Assessments**

Classification	Examination Component	Unit	Rounding Digit / Categories
Hematology	Hemoglobin	[g/dL]	0.1
	Hematocrit	[%]	0.1
	Platelet Count	[ $\times 10^{10}/L$ ]	0.1
	Red Blood Cells	[ $\times 10^{10}/L$ ]	1
	Leukocyte Total	[/ $10^6/L$ ]	1
	Neutrophils	[%]	0.1
	Lymphocytes	[%]	0.1
	Basophils	[%]	0.1
	Eosinophils	[%]	0.1
	Monocytes	[%]	0.1
	IgG	[mg/dL]	1
	IgA	[mg/dL]	1
	IgM	[mg/dL]	1
	Coagulation Profile (APTT)	[sec]	0.1
Biochemistry	Aspartate Aminotransferase (AST)	[IU/L]	1
	Alanine Aminotransferase (ALT)	[IU/L]	1
	Direct Bilirubin	[mg/dL]	0.1
	Total Bilirubin	[mg/dL]	0.1
	Uric Acid	[mg/dL]	0.1
	Alkaline Phosphatase	[U/L]	1
	Total Protein	[g/dL]	0.1
	Albumin	[g/dL]	0.1
	Prothrombin Time/International Normalized Ratio (PT-INR)	-	0.01
	Fibrinogen	[mg/dL]	1
	Complement C3	[mg/dL]	1

Urinalysis	Complement C4	[mg/dL]	1
	Cardiac Troponin	[ng/L]	0.1
	Creatinine	[mg/dL]	0.01
	C-reactive protein (CRP)	[mg/dL]	0.01
	Sodium	[mEq/L]	1
	Potassium	[mEq/L]	0.1
	Calcium	[mg/dL]	0.1
	Glucose	[mg/dL]	1
	Triglycerides	[mg/dL]	1
	HDL	[mg/dL]	1
	LDL	[mg/dL]	1
	BUN/Urea	[mg/dL]	0.1
	Erythrocytes	-	- , +- , + , 2+ , 3+ , 4+
	Leukocytes	-	- , +- , + , 2+ , 3+ , 4+
	Glucose	-	- , +- , + , 2+ , 3+ , 4+
	Ketones	-	- , +- , + , 2+ , 3+ , 4+
	pH	-	0.1
	Protein	-	- , +- , + , 2+ , 3+ , 4+
	Erythrocytes (Sediment) a)	-	
	Leukocytes (Sediment) a)	-	
	Protein (Sediment) a)		

a) Erythrocytes (Sediment), Leukocytes (Sediment), Protein (Sediment) will be shown only in listings.

### 15.3.1 Descriptive Statistics of Laboratory Parameters

Population: Safety Analysis population

Group: Emapalumab, Placebo

Contents:

- Calculate the descriptive statistics of quantitative laboratory parameters (in Table 7 in Section 15.3 Laboratory data) at each analysis time point (defined in Table 3 in Section 8.4.3 Visit Windows) by groups.
- Conduct the same analysis by treatment groups and grades (Low/Normal/High).
- Conduct the same analysis for change from baseline.

### **15.3.2      Figure of Laboratory Parameters Versus Time Curves of Individual Subject**

Population: Safety Analysis population

Group: Emapalumab, Placebo

Contents: 

- Create XY plots of quantitative laboratory parameters (in Table 7 in Section 15.3 Laboratory data) at actual time points by groups.
- X axis: Actual time points observed
- Y axis: Quantitative laboratory parameters (Show each name of quantitative laboratory parameters in Table 7 in Y axis label)

### **15.3.3      Contingency Table of Urine Parameters**

Population: Safety Analysis population

Group: Emapalumab, Placebo

Contents: 

- Create cross tables of qualitative urine parameters (in Table 7 in Section 15.3 Laboratory data) of baseline and at each analysis time point after IMP administration (defined in Table 3 in Section 8.4.3 Visit Windows) by groups.
- Remove data from calculation if both data from before and after IMP administration do not exist.

### **15.3.4      Contingency Table of Laboratory Parameters**

Population: Safety Analysis population

Group: Emapalumab, Placebo

Contents: 

- Create cross tables of normal range grading (Low/Normal/High) of quantitative laboratory parameters (in Table 7 in Section 15.3 Laboratory data) of baseline and at each analysis time point after IMP administration (defined in Table 3 in Section 8.4.3 Visit Windows) by groups.
- Remove data from calculation if both data from before and after IMP administration do not exist.

## 15.4 Anti-drug antibodies

The list of immunogenicity evaluated in this study is presented in Table 8.

**Table 8 List of Immunogenicity Assessments**

Examination Component	Unit	Rounding Digit / Categories
Anti-drug antibodies (ADAs)	-	Positive, Negative
Neutralizing antibodies (nAbs)	-	Positive, Negative

### 15.4.1 The presence of ADAs and nAbs

Population: PK/PD population

Group: Emapalumab, Placebo

Contents:

- Calculate the number of subjects with positive with ADA/nAbs in Table 8 in 15.4 Anti-drug antibodies at baseline and at study completion or withdrawal (defined in Table 3 in 8.4.3 Visit Windows) by groups.
- Denominator to calculate the percentages: The number of subjects from the population in each group.

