6.5.4 Replacement of withdrawn subjects

Subjects who withdrawn from the study after IMP administration will not be replaced. Subjects who withdraw from the study prior to IMP administration will be replaced to ensure that 8 subjects, i.e. 6 who receive emapalumab and 2 who receive placebo.

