### 7.2 PK/PD Analysis population

A PK/PD population will be used for analyzing the primary endpoints. This population comprises all randomized subjects who received an infusion of Emapalumab, without any protocol deviations affecting PK/PD evaluation. All analyses using the PK/PD population will group subjects according to treatment actually received.

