### 8.3.2 Percentages

Percentage is calculated using the following formula (unless otherwise indicated):

$$\text{Percentage (\%)} = \frac{\text{the number of applicable subjects}}{\text{the number of subjects within the treatment group for the population of interest}} \times 100$$

Percentages will be suppressed when the count is zero, however the category will still be displayed.

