## 10 Demographics and baseline characteristics

### 10.1 Demographics and Other Baseline Characteristics

Population: Safety Analysis population, PK/PD Analysis population

Group: Emapalumab, Placebo

Contents:

- For categorical data and ordinal data, calculate the number of subjects and percentages.
- For continuous data, calculate the descriptive statistics.

Definitions:

- BMI  
BMI at screening will be calculated using the following formula:

$$\text{BMI} = \frac{\text{Weight [kg]}}{(\text{Height [m]})^2}$$

- Unknown and Missing values  
If unknown or missing values are observed, add “Unknown” category and only calculate the number of subjects. Remove “Unknown” category from the denominator for percentages.
- Race is only displayed in the listing.

[Background Factors]

Classification [Unit]	Category
Age [Year]	<30, 30≤ <40, 40≤
	Descriptive statistics
Sex	Male, Female
Height [cm]	Descriptive statistics
Weight [kg]	Descriptive statistics
BMI [kg/m  ]	Descriptive statistics

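### The ADA/nAb percentages in SAP 15.4.1 divide by everyone in the population rather than everyone tested, and the unpaired visit counts do not show treatment-emergent ADA

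*SAP*

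**What the plan says.** SAP 15.4.1 counts the subjects positive for ADA or nAb "at baseline and at study completion or withdrawal", by group (Emapalumab, Placebo), in the PK/PD population. The divisor is given as "Denominator to calculate the percentages: The number of subjects from the population in each group". This follows the SAP's general rule in 8.3.2, where the divisor is "the number of subjects within the treatment group for the population of interest".

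On who is in that population, SAP 7.2 says: "This population comprises all randomized subjects who received an infusion of Emapalumab". The only further condition is that no protocol deviation affects the PK/PD evaluation. An immunogenicity sample is not a condition.

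SAP Table 8 allows two results, "Positive, Negative". It has no category for a missing or non-evaluable result, no titer and no treatment-emergent class. The missing-data rules in SAP 8.6 deal only with adverse events.

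Protocol 6.7.7 plans two immunogenicity samples per subject, one before the infusion and one at study completion. Protocol 6.7.1.5 asks for the completion-visit assessments at a withdrawal visit too. Protocol 6.5.4 says: "Subjects who withdrawn from the study after IMP administration will not be replaced". SAP 16 plans a subject listing of ADA and nAb results.

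**The concern.** Two features of the table matter.

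First, a dosed subject without a post-dose result stays in the denominator and cannot enter the numerator. That subject lowers the percentage exactly as a tested negative would. There is only one scheduled post-dose sample, so a subject who misses it has no other post-dose result to fall back on. SAP 9.1 itself lists loss to follow-up among the reasons for discontinuation.

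Second, positives are counted separately at each visit, with no condition on baseline status. A subject who is positive before dosing and still positive at Week 14 is counted at both visits. The secondary objective is the immunogenicity of emapalumab, which depends on who became positive after dosing. Two separate counts do not give that.

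The SAP already pairs baseline with post-dose results elsewhere. Urinalysis (15.3.3), quantitative laboratory values (15.3.4), physical examination (15.6.1) and ECG (15.7.1) all have cross tables and a rule for unpaired data. ADA/nAb is a named secondary endpoint and has neither.

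**Working it through.** **Inputs.** Eight subjects randomized 3:1 (protocol 6.1; SAP 4.3): 8 × 3/4 = 6 emapalumab and 8 × 1/4 = 2 placebo. The documents give no expected ADA percentage for this trial. The nearest figures, in protocol 4.4, reproduce: 1/14 = 7.1% in healthy subjects and 3/49 = 6.1% in HLH patients. The numbers of positive and missing results below are assumptions.

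**Denominator.** SAP percentage = x/6. Percentage of those tested = x/(6 − m), where x is the number positive at Week 14 and m is the number of missing samples.

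| Positive x | Missing m | SAP x/6 | Of those tested |
|---|---|---|---|
| 1 | 0 | 16.7% | 1/6 = 16.7% |
| 1 | 1 | 16.7% | 1/5 = 20.0% |
| 1 | 2 | 16.7% | 1/4 = 25.0% |
| 2 | 1 | 33.3% | 2/5 = 40.0% |
| 2 | 2 | 33.3% | 2/4 = 50.0% |
| 0 | any | 0 | 0 |

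With no positives, the two rules agree whatever is missing.

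**Pairing.** Treatment-emergent percentage = new positives ÷ (subjects negative at baseline and tested post-dose). Take six subjects, none missing, and one positive at baseline, so that five are negative at baseline.

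- The baseline positive persists and nobody is new: SAP Week 14 = 1/6 = 16.7%; treatment-emergent = 0/5 = 0%.
- The baseline positive persists and one is new: SAP Week 14 = 2/6 = 33.3%; treatment-emergent = 1/5 = 20.0%.
- The baseline positive turns negative and one is new: SAP Week 14 = 1/6 = 16.7%; treatment-emergent = 1/5 = 20.0%.

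The first and third cases print the same row, 1/6 at baseline and 1/6 at completion, yet their treatment-emergent results are 0% and 20.0%.

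**Placebo column.** SAP 15.4.1 lists a Placebo group, but SAP 7.2 admits only emapalumab recipients. Both placebo subjects fall outside the population, so that column has a denominator of 0.

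**The case against.** The best defence is that the plan does what it says. The endpoint is the presence of antibodies, and protocol 8.3.4.3 asks for number and percentage at baseline and post-baseline. SAP 15.4.1 delivers this and shows baseline positives as their own count. Neither document calls the Week 14 figure drug-induced, so a reader who infers that it is mislabelled goes beyond the text. A subject positive at Week 14 is correctly counted as present. The gap is that the table stops short of what the objective needs.

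A reader might also infer a breach of protocol 8.3.8, "No imputations of missing data will be performed". The documents do not support that. SAP 15.4.1 assigns no value to a missing result; it counts positives and divides by the group size, which is the SAP's general convention. SAP 10.1 does remove its unknown "category from the denominator for percentages", but that rule belongs to the demographics table, so the difference is one of practice and not a contradiction.

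Nor does the percentage go wrong every time a sample is missing or an antibody was already present. The first effect needs at least one positive subject; the second needs a baseline positive who is still positive at Week 14.

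Two safeguards also stand. Withdrawal visits include the same sampling, which limits missing results. With six active subjects, the listing shows who was tested and who was newly positive. No hypothesis test depends on the figure. These points limit the impact, but a prespecified summary should not need correcting by hand.

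**Conclusion.** The point holds in a limited form. The divisor in SAP 15.4.1 includes subjects with no sample at the time point, and the unpaired counts cannot show treatment-emergent ADA. With one positive of six, the denominator effect is 16.7% against 20.0% with one sample missing and 25.0% with two. The pairing effect is 16.7% against 0/5 when a single baseline positive persists and nobody is new. The two effects act in opposite directions: a missing sample lowers the percentage, and a persistent baseline positive raises it above the treatment-emergent figure. All of this rests on assumed counts. If no sample is missing and nobody is positive at baseline, the planned percentage equals the corrected one. The empty Placebo column does not depend on any assumption. The change is worth making because it is cheap and serves a stated secondary objective; the conduct of the trial is not in question.

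**What to change.** In SAP 15.4.1:

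- Use the number of subjects with an evaluable ADA result at that time point as the denominator for both the ADA and the nAb percentages, and show that n. If nAb is run only on ADA-positive samples, count ADA-negative subjects as nAb-negative. The wording of protocol 6.7.7 leaves that possibility open, and a denominator of nAb-tested subjects could then turn 1/6 into 1/1.
- Add a row for treatment-emergent ADA (negative at baseline, positive post-dose), with subjects negative at baseline and tested post-dose as its denominator. Show baseline-positive subjects separately.
- Base the table on the Safety Analysis population. This fills the Placebo column and keeps emapalumab subjects whose only problem is a deviation affecting PK/PD.

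The cost is a few lines of SAP text and the added rows, all from data already collected. The downside is a slightly smaller denominator when a sample is missing.
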